4.2 Treatment duration

- Patients in CRi or PR post-transplant will be treated until disease progression or unacceptable toxicity.
- Patients in CR or CRc post-transplant will be treated for 24 cycles, then:
 - o Patients who are MRD-positive or have different characteristics that, in the opinion of the investigator, put them at a high-risk of relapse, may continue to receive treatment as long as they continue to derive benefit and remain in remission.
 - o Patients who are MRD-negative and don't have other characteristics indicative of high-risk of relapse will stop treatment after 24 cycles, unless the Investigator has a reason to continue treatment (for example, conversion from MRD-positive to MRD-negative only shortly before the 24th cycle).

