8.0 Statistical Considerations

Type of study: Open label, single-arm, single center, Phase 2 clinical trial

Number of patients planned: 20

Expected accrual rate: 5-10 patients/year

Toxicity monitoring

Continuous monitoring of toxicity will be performed in all 20 patients. The first 3 patients will be treated with 9 mcg/kg in first 4 cycles. From cycle 5 and beyond in the first 3 patients, the dose will be 12 ug/kg/day. All subsequent patients will be treated with 12 ug/kg/day. Unacceptable toxicities are defined as tagraxofusp-related toxicities which prevent initiation of Cycle 2 of therapy (Any adverse event ³ grade 3 that is both a) considered related to tagraxofusp, and b) does not resolve to \leq grade 2 after a maximum delay of 56-days). Assuming a prior beta distribution of (0.4, 1.6), corresponding to an unacceptable toxicity rate of 30%, treatment will terminate if the $Pr(dt > 0.20 | \text{data}) > 0.95$, where dt is the toxicity rate attributable to the tagraxofusp treatment. The decision rule for terminating for toxicity is presented in Table 4 and the software used for this Bayesian toxicity monitoring rule is Multc Lean version 2.1.0. The operating characteristics for this rule are presented in Table 5. The method used to produce the decision rule and operating characteristics was designed by Thall, Simon, and Estey ^{26, 27} and extended by Thall and Sung. ²⁸

Table 4 Stopping criteria

Total Patients Enrolled	Stopping Condition (# of patients experiencing unacceptable toxicities)
3-4	3-4
5-8	4-8
9-11	5-11
12-14	6-14
15-18	7-18
19	8-19
20	Patient enrollment ends

Table 5 Operating characteristics

True % of DLTs	Pr (stopping early)	Average # of patients treated
0.05	0.00	20
0.10	0.01	20
0.20	0.11	19
0.30	0.38	16
0.40	0.70	12
0.50	0.91	9

Analysis

Demographic and baseline characteristics will be summarized. Categorical measures will be summarized using frequencies and percentages while continuous variables will be summarized using mean, standard deviation, median, minimum, and maximum.

The primary endpoint of the study is the tolerability of tagraxofusp post-SCT, where tolerability is defined as receipt of at least 75% of planned tagraxofusp doses in at least 4 cycles of therapy. The following table shows the exact 95% confidence intervals for different percentages of patients, out of 20 patients, experiencing tolerability:

Patients experiencing tolerability		95% Exact
Number	Percentage	Confidence Interval
2	10%	1.2% - 31.7%

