5	25%	8.7% - 49.1%
10	50%	27.2% - 72.8%
15	75%	50.9% - 91.3%

The percentage of patients considered 'tolerating' by this definition will be presented along with the associated 95% exact confidence interval.

PFS is defined as the duration from treatment start date to date of disease progression or death. Patients who are still alive at the end of the study with no evidence of disease will be censored. OS is defined as the time from treatment start date to death. Patients who are still alive at the end of the study will be censored. PFS and OS will be estimated using the Kaplan-Meier method. Median PFS and OS as well as rates with corresponding 95% confidence intervals will be presented.

Summary Reports

The Investigator is responsible for completing a toxicity/tolerability summary report, and submitting it to the IND Office Medical Affairs and Safety Group, for review and approval. This should be submitted after the first 3 evaluable patients, complete 1 cycle of study treatment, and every 2-3 evaluable patients, thereafter, following Table 4 stopping criteria guidelines.

For tolerability, an updated summary report should be submitted every 2-5 patients complete 4 cycles of study therapy, in accordance to the table located in the "Analysis" section of the protocol.

A copy of the toxicity summary should be placed in the Investigator's Regulatory Binder under "sponsor correspondence".

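### As worded, the only numeric trial-level toxicity rule counts Cycle 1 events, while the primary endpoint needs at least 4 cycles and planned treatment is 24 cycles or open-ended

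*Combined protocol and SAP*

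**What the plan says.** **The counted event.** Section 8.0 (Toxicity monitoring) states: "Continuous monitoring of toxicity will be performed in all 20 patients". It then defines the event: "Unacceptable toxicities are defined as tagraxofusp-related toxicities which prevent initiation of Cycle 2 of therapy". A parenthesis adds that the event is grade 3 or higher, related to the drug, and not resolved to grade 2 or lower "after a maximum delay of 56-days". The parenthesis names no cycle. Table 4 gives the number of patients with this event that stops the trial, and Table 5 gives the probability of stopping.

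**When it is reviewed.** Under Summary Reports in Section 8.0, the toxicity report tied to Table 4 is due once the first 3 evaluable patients have completed 1 cycle, and then every 2-3 evaluable patients. A second report follows: "For tolerability, an updated summary report should be submitted every 2-5 patients complete 4 cycles of study therapy". It refers to the table of exact confidence intervals, which contains no stopping threshold.

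**How long treatment lasts.** Section 4.2: "Patients in CR or CRc post-transplant will be treated for 24 cycles, then" stop or continue according to MRD status and relapse risk. Patients in CRi or PR have no fixed end. The primary endpoint in Section 8.0 is receipt of at least 75% of planned doses in at least 4 cycles.

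**Where else the definition is used.** Section 4.4 makes the first three patients' move to 12 mcg/kg at Cycle 5 depend on no unacceptable toxicity at 9 mcg/kg, as defined in the statistical section. Those patients receive 9 mcg/kg in Cycles 1-4.

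**The concern.** The primary objective is the safety of repeated dosing after transplant. If the definition is followed literally, a patient who starts Cycle 2 is a non-event for Table 4 from then on, whatever happens later. Cycles 2-4 of the primary endpoint window, and every later cycle, then have no numeric trial-level boundary. For patients 1-3, all dosing at 12 mcg/kg lies outside the rule.

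The 4-cycle report does not close this gap. It sets no boundary, and it is triggered by patients who complete 4 cycles, so a patient lost to toxicity in Cycle 2 or 3 does not trigger it. At stake is how Table 5 is read: its stopping probabilities describe protection against the Cycle 1 event, not protection over the period that the primary endpoint covers.

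**Working it through.** **Inputs from Section 8.0.** 20 patients; Beta(0.4, 1.6) prior; stop if the posterior probability that the toxicity rate exceeds 0.20 is above 0.95; accrual of 5-10 patients per year. Section 4.4 gives a 28-day cycle.

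**Step 1: reproduce Table 4.** With x events in n patients the posterior is Beta(0.4 + x, 1.6 + n − x). The boundary is the smallest x with Pr(rate > 0.20) > 0.95. For example, at n = 5, x = 3 gives 0.948 (continue) and x = 4 gives 0.993 (stop). At n = 19, x = 7 gives 0.941 and x = 8 gives 0.979. For n = 3 to 19 the boundaries are 3 (n = 3-4), 4 (5-8), 5 (9-11), 6 (12-14), 7 (15-18) and 8 (19), exactly as in Table 4. (The prior mean is 0.4/2.0 = 20%, not the 30% stated. That is a separate point and does not affect this check.)

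**Step 2: reproduce Table 5.** An exact binomial recursion over these boundaries, with a look after each of patients 3-19, gives:

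| True rate of counted event | Pr(stop), computed | Table 5 |
|---|---|---|
| 0.05 | 0.0008 | 0.00 |
| 0.10 | 0.0092 | 0.01 |
| 0.20 | 0.1083 | 0.11 |
| 0.30 | 0.3764 | 0.38 |
| 0.40 | 0.7007 | 0.70 |
| 0.50 | 0.9104 | 0.91 |

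The tables are internally sound. The question is only which event the true rate refers to.

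**Step 3: coverage.** On the Cycle 1 reading the rule covers 1 of the 4 cycles that the primary endpoint needs at a minimum, and 1 of 24 planned cycles (24 × 28 = 672 days) in CR/CRc patients, plus the permitted delay.

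**Step 4: illustration.** The documents give no per-cycle rates, so these are assumptions. Let p be the Cycle 1 rate and q the rate of related treatment-ending toxicity in each of Cycles 2-4 among patients continuing. The cumulative rate is 1 − (1 − p)(1 − q)³. For p = 0.10 and q = 0.08: 1 − 0.90 × 0.92³ = 1 − 0.90 × 0.7787 = 0.299. The Step 2 recursion is run at p (as written) and at the cumulative rate (Cycles 1-4 counted):

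| p | q | Cumulative | As written | Cycles 1-4 counted (upper bound) |
|---|---|---|---|---|
| 0.05 | 0.05 | 0.185 | 0.001 | 0.084 |
| 0.10 | 0.08 | 0.299 | 0.009 | 0.374 |
| 0.10 | 0.15 | 0.447 | 0.009 | 0.819 |

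With no Cycle 1 events the rule as written stops with probability 0, whatever happens later.

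**Step 5: allow for timing.** The last column assumes that each patient's 4-cycle outcome is known at every look, but four cycles take 4 × 28 = 112 days. The middle row was simulated with random staggered entry, a look at each enrolment, and events known at the end of their cycle. Pr(stop) is about 0.32 at 5 patients per year and 0.27 at 10. If a further 56 days pass before an event counts, it is about 0.27 and 0.19. The contrast with 0.01 remains.

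**The case against.** **The scope of the event is ambiguous.** The parenthesis names no cycle, monitoring is called continuous, and Section 4.4 applies the same definition to 9 mcg/kg dosing that spans Cycles 1-4. The drafters may have meant more than Cycle 1. This stands in part: it cannot be said with certainty that later events are excluded. But the parenthesis explains a clause about starting Cycle 2, and the Table 4 report follows one cycle, so the operative wording favours the Cycle 1 reading. If the wider one was meant, the text still needs correcting.

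**Later toxicity is not unwatched.** A reader might infer that a related death in Cycle 6 would go unnoticed. The documents do not support that. Section 6.1 sends all SAEs to the IND Office within 5 working days, and unexpected, related life-threatening or fatal events within 24 hours (next working day). Summary reports go to the IND Office for review and approval, and Section 4.7 ends treatment for individuals. What is missing is a trial-level boundary.

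**The 20% limit belongs to the counted event.** A reader might infer that 30% toxicity over four cycles breaches the plan's own limit. It does not: 0.20 was set for the event that Table 4 counts, and the plan sets no acceptable rate for 4-cycle toxicity.

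**A first-cycle window is a recognisable design choice.** That is fair. It sits poorly here only because safety is the primary objective, the primary endpoint needs at least 4 cycles, and no other provision sets a threshold.

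**Conclusion.** The concern holds in a limited form. On its operative wording, the only numeric trial-level toxicity rule counts related toxicity that prevents Cycle 2. Table 5 therefore describes protection against that event alone, and Sections 4.4 and 8.0 do not agree clearly on which cycles count.

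Under the assumed rates of 10% in Cycle 1 and 8% in each of Cycles 2-4, the rule as written stops with probability 0.01. Counting Cycles 1-4 on the same boundaries would give at most 0.37, and about 0.19-0.32 with staggered entry at 5-10 patients per year and a lag of 0-56 days. The size depends wholly on the assumed rates. The structural gap does not. The illustration shows sensitivity; it is not evidence that later toxicity will be high.

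**What to change.** 1. State in Section 8.0 which cycles the event definition covers, and reconcile Section 4.4, the toxicity monitoring text and the Summary Reports text accordingly.
2. Keep the Cycle 1 tally. Add a second trial-level tally of patients with a tagraxofusp-related death, or a related toxicity that permanently ended treatment, in Cycles 1-4, reviewed at each summary report. The sponsor should confirm the acceptable 4-cycle rate. Table 4 can be reused if that rate is 20%; otherwise new boundaries are needed. Report operating characteristics for the combined rule, with staggered entry.
3. Trigger the 4-cycle report by patients who have completed 4 cycles or stopped earlier. In the same reports, list related deaths and treatment-ending toxicities from Cycle 5 on, including those in patients 1-3 after the move to 12 mcg/kg. The Cycle 1-4 tally does not cover these later events, so listing them gives visibility but no boundary.

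**Cost.** The change needs protocol wording, a sponsor decision on the acceptable rate, and new operating characteristics. Event grade and attribution are already recorded. The chance of stopping early rises: with a 10% Cycle 1 rate and a true 4-cycle rate of 20%, it goes from about 0.01 to at most about 0.11 on the Table 4 boundaries (Step 2, rows 0.10 and 0.20, taking every Cycle 1 event as also counted in the second tally). Whether that is acceptable is for the sponsor to judge.

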4.4 Dose and schedule

First three patients:

- Cycles 1-4: Tagraxofusp 9 mcg/kg IV on Days 1, 2, and 3.
- Cycles 5 and beyond: Tagraxofusp 12 mcg/kg IV on Days 1 and 2 (if no unacceptable toxicities at the 9 ug/kg/day IV dose, as defined in the statistical section).

Patient number 4 and beyond:

- Cycles 1-4: Tagraxofusp 12 ug/kg/day IV on Days 1, 2, and 3.
- Cycles 5 and beyond: Tagraxofusp 12 ug/kg/day IV on Days 1 and 2.

Cycle Length: 28 days

During a 28-day cycle, if the patient experiences related non-hematological toxicity with resolution to Grade ≤ 1 or baseline by day 28, the tagraxofusp dose may be continued during the next cycle at the same dose.

Otherwise tagraxofusp-related non-hematological toxicity not resolved to Grade ≤ 1 or baseline by day 28, the start of the next cycle will be delayed until resolution to Grade ≤ 1 or baseline up to a maximum of additional 28 (56 total) days.

After this treatment delay dosing may be continued during the next cycle at same dose.

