4.6 Dose modifications for tagraxofusp related hematological toxicity

It is often very challenging to differentiate disease-related from treatment-related hematological toxicities in patients with BPDCN. Patients with neutropenia, anemia, or thrombocytopenia as a consequence of their disease do not require treatment interruptions for myelosuppression. Dose-interruptions in these patients should be considered on a case-by-case basis and discussed with the PI.

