4.7 Discontinuation of treatment

Treatment will continue until maximal duration of maintenance therapy is reached (as specified in Section 4.0, Treatment Duration), or the occurrence of any of the following events:

- Disease progression
- Adverse event(s) that, in the judgment of the Investigator/Medical Monitor, may cause severe or permanent harm or which rule out continuation of maintenance study drug.
- Graft failure
- Development of grade III-IV acute GVHD
- Development of severe chronic GVHD
- Suspected pregnancy
- Inability to start planned cycle of tagraxofusp within 56 days of intended start date of each cycle.
- Major violation of the study protocol (to include subject noncompliance with study medications or protocol-specified procedures) at the discretion of the PI

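### Section 8 counts as unacceptable toxicity only part of what the protocol's own rules say prevents Cycle 2, and the delay limit and Cycle 5 dose condition tied to it do not work as written

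*Combined protocol and SAP*

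**What the plan says.** Section 8.0 (Toxicity monitoring) opens its definition with "Unacceptable toxicities are defined as tagraxofusp-related toxicities which prevent initiation of Cycle 2 of therapy". A parenthetical then describes a related adverse event of grade 3 or higher (the symbol is garbled in the text and is read here as ≥) that does not resolve to at most "grade 2 after a maximum delay of 56-days". Table 4 counts patients with this event.

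Four other places decide whether Cycle 2 starts:

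- Section 4.4 holds the next cycle until grade 1 or baseline: "Otherwise tagraxofusp-related non-hematological toxicity not resolved to Grade ≤ 1 or baseline by day 28" triggers a delay, "up to a maximum of additional 28 (56 total) days".
- Section 4.8, Table 3 requires permanent discontinuation after severe or life-threatening hypersensitivity, whether or not it resolves.
- Section 4.7 stops treatment for adverse events that in the investigator's or medical monitor's judgment "may cause severe or permanent harm or which rule out continuation of maintenance study drug".
- Section 4.7 also stops treatment for "Inability to start planned cycle of tagraxofusp within 56 days of intended start date of each cycle".

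Section 4.4 reuses the Section 8 definition for the first three patients. They move from 9 to 12 mcg/kg at Cycle 5 "if no unacceptable toxicities at the 9 ug/kg/day IV dose, as defined in the statistical section". Section 8 states the same dose increase without the condition.

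**The concern.** The lead clause and the parenthetical set different thresholds, and nothing says which governs. A toxicity can keep a patient from ever receiving Cycle 2 and still not be counted. Safety is the primary objective, and this count is the sole input to the Table 4 rule and to the toxicity summary reports that follow it. With at most 20 patients and stopping counts of 3 to 8, the classification of a single patient can decide whether the trial continues.

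The same wording is also the only stated toxicity condition on raising the dose of the first three patients, so a gap in it carries over to that decision.

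**Working it through.** **1. Does the parenthetical match the rules that prevent Cycle 2?** Take a tagraxofusp-related toxicity arising in Cycle 1:

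| Case | Prevents Cycle 2? | Meets the parenthetical? |
|---|---|---|
| Grade ≥3, still ≥3 when the window closes, non-hematological | Yes (4.4, 4.7) | Yes |
| Non-hematological, at grade 2 and above baseline when the window closes | Yes (4.4 needs grade ≤1 or baseline) | No |
| Severe or life-threatening hypersensitivity that resolves | Yes (Table 3) | No |
| Stopped by judgment, later improves to grade ≤2 | Yes (4.7) | No |

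The baseline exception seldom rescues the second row, because Section 3.2 already excludes most patients with persistent clinically significant non-hematological toxicity of grade 2 or more.

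**2. Delay limit, in days from the start of a 28-day cycle.**

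- Section 4.4: 28 + 28 = day 56.
- Section 4.7: 28 + 56 = day 84.
- Section 8: a maximum delay of 56 days with no starting point. It is most naturally day 84, but day 56 is possible.

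A non-hematological toxicity that reaches grade 1 on day 70 is too late under Section 4.4 and in time under Section 4.7.

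**3. Cycle 5 condition.** A patient at Cycle 5 has started Cycle 2. Such a patient cannot have had a toxicity that prevented Cycle 2, so the condition is always met when applied to each patient. Applied to the three together it has content, since an event in one patient could bar the increase in the others. The text does not say which is meant.

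**4. Reproduce the plan's figures.** Inputs from Section 8: prior Beta(0.4, 1.6), limit 0.20, cutoff 0.95, maximum 20 patients. With k events in n patients, stop if Pr(rate > 0.20) > 0.95 under Beta(0.4 + k, 1.6 + n − k). This gives every Table 4 boundary from n = 3 to 19. Exact recursion over those boundaries gives early-stopping probabilities of 0.001, 0.009, 0.108, 0.376, 0.701 and 0.910 at true rates of 0.05, 0.10, 0.20, 0.30, 0.40 and 0.50, which match Table 5. (The prior mean is 0.4/2.0 = 20%, not the stated 30%. That is a separate matter and does not affect this point.)

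**5. What one patient does.** Over the 17 sample sizes, the stopping count gives a posterior of 0.950 to 0.993, and one patient fewer gives 0.825 to 0.948. For example, 3 of 4 gives 0.973 (stop) and 2 of 4 gives 0.846 (continue). Any count rule behaves this way. The figures show only that a disputed classification can decide the outcome.

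**6. Illustration of under-counting.** Suppose the parenthetical counts a share f of the patients whom related toxicity keeps from Cycle 2. The value of f is an assumption, since the documents give none. The counted rate is then f × true rate; for example, 0.75 × 0.30 = 0.225. Cells show Pr(stop early), with mean patients treated in brackets:

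| True rate | f = 1 | f = 0.9 | f = 0.75 | f = 0.5 |
|---|---|---|---|---|
| 0.20 | 0.11 (18.8) | 0.08 (19.1) | 0.04 (19.5) | 0.01 (19.9) |
| 0.30 | 0.38 (16.0) | 0.28 (17.0) | 0.16 (18.3) | 0.04 (19.5) |
| 0.40 | 0.70 (12.2) | 0.58 (13.7) | 0.38 (16.0) | 0.11 (18.8) |

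**The case against.** The best defence is that there is one definition: the parenthetical follows directly on the Cycle 2 clause and spells it out, and counting only persistent severe toxicity is a legitimate choice for a stopping rule. The choice is legitimate. It does not, however, remove the mismatch, because the sentence says it counts toxicities that prevent Cycle 2 and then applies a resolution threshold one grade looser than the rule that decides whether Cycle 2 starts.

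The defence does defeat some stronger readings.

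- A reader might infer that the parenthetical, naming no cycle, brings later-cycle events into Table 4. Its place in the sentence points to Cycle 2, and the first toxicity report is due when three evaluable patients complete one cycle.
- A reader might infer that it counts many persistent cytopenias while Cycle 2 goes ahead. If Cycle 2 starts on time, no maximum delay has run. The Section 4.6 wording, "Dose-interruptions in these patients should be considered on a case-by-case basis and discussed with the PI", concerns patients whose cytopenias come from their disease. Section 6.0 further narrows which laboratory changes and post-transplant events are adverse events at all. The 35% thrombocytopenia figure in Section 2.3.2 is any-grade and does not settle how often this occurs.
- A reader might take the illustration as an estimate. It is not: f is unknown, and at low rates the effect is small (a true 15% counted as 10% moves the stopping probability from 0.039 to 0.009).

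Safeguards also stand. All serious adverse events go to the IND Office, which also reviews and approves each summary. The Cycle 5 condition concerns at most three patients, and Sections 4.4 and 4.7 continue to apply to them at every cycle. These limit the harm, but the summaries themselves are to follow Table 4, so they take over its event definition.

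**Conclusion.** The point holds. Section 8's parenthetical omits three kinds of patient whom the protocol's own rules keep from Cycle 2. If it governs, Table 4 under-counts relative to the lead clause. The delay limit is inconsistent (day 56 against day 84, with Section 8 unanchored), and the Cycle 5 condition is empty when applied patient by patient.

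The size cannot be derived, because the documents give no rate for the affected events. Severe hypersensitivity is probably the smallest part, since no hypersensitivity term appears in the table of events at 10% or more. Tables 4 and 5 are arithmetically sound for whatever event is counted, so a reader should not infer that the boundaries are wrong. Nor is the primary analysis compromised: a patient who never starts Cycle 2 cannot receive the required doses in at least four cycles and is classed as not tolerating on either reading. This is a safety-definition defect worth correcting, with medium confidence in its practical weight.

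**What to change.** 1. **Table 4 event.** Count a patient when a tagraxofusp-related toxicity arising in Cycle 1 (a) prevents Cycle 2 from starting within the delay window under Section 4.4, (b) leads to permanent discontinuation under Section 4.7 or Table 3, or (c) leads to death. Also count (d) a related grade ≥3 event from Cycle 1 that has not resolved to grade ≤2 by the end of that window. Keep the event to Cycle 1. Counting events in every cycle would make it cumulative over 24 or more 28-day cycles, many events would arrive after later patients had enrolled, and Table 5 would no longer describe the rule.
2. **Delay window.** Use one limit in Sections 4.4, 4.7 and 8, stated as days after the intended start of the next cycle.
3. **Cycle 5 dose increase.** State a separate condition covering related toxicity in Cycles 1-4 at 9 mcg/kg, say whether it applies to each patient or to the three together, and carry it into Section 8.

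The cost is a wording amendment; Tables 4 and 5 do not change. Because the event is somewhat wider, the rule may stop slightly more often, and the team should confirm that the 20% limit suits it.

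### Table 4 is tied to two different denominators with no rule for pending outcomes, so the stopping probabilities in Table 5 are not assured at the stated accrual rate

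*Combined protocol and SAP*

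**What the plan says.** Section 8.0 promises that "Continuous monitoring of toxicity will be performed in all 20 patients". The rule terminates treatment when the posterior probability that the toxicity rate exceeds 0.20 is above 0.95, under a Beta(0.4, 1.6) prior. Table 4 turns this into counts. Its first column is headed "Total Patients Enrolled", and its row for 20 gives no count, only "Patient enrollment ends". Table 5 gives the operating characteristics.

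The event being counted is a tagraxofusp-related toxicity that prevents the start of Cycle 2 and has not resolved sufficiently "after a maximum delay of 56-days". Section 4.4 allows the next cycle to be delayed "up to a maximum of additional 28 (56 total) days". Section 4.7 counts 56 days from the intended start of the cycle.

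The Summary Reports paragraph at the end of Section 8.0 uses Table 4 differently. The first report comes after 3 evaluable patients complete one cycle, and later ones after every 2-3 evaluable patients. Evaluable is not defined there.

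On accrual, the plan states "Expected accrual rate: 5-10 patients/year". It does not say whether enrolment continues while outcomes are pending.

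**The concern.** A toxicity may take much longer to confirm than a new patient takes to arrive. If the denominator is patients enrolled, patients still under observation count as if they were free of toxicity, and a higher count is needed to stop. For example, take 8 patients with known outcomes, 4 of them toxic, and 2 more enrolled with outcomes pending. Read by known outcome, Table 4 stops (4 of 8). Read by enrolment, it continues (10 enrolled needs 5).

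The evaluable wording does not settle the matter. A patient completes Cycle 1 at about day 28, but an unresolved event may be confirmed only weeks later. That patient can enter the denominator before the event enters the numerator.

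Safety is the primary objective and Table 5 is the stated safety property of the design. If the rule is run in a way that Table 5 does not describe, more patients may be exposed before stopping than the plan states.

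**Working it through.** **Inputs.** From Section 8.0: Beta(0.4, 1.6), limit 0.20, cutoff 0.95, 20 patients, 5-10 patients per year. From Section 4.4: 28-day cycle. The text describes the prior as a 30% rate, but its mean is 0.4/(0.4 + 1.6) = 0.20. Table 4 follows the stated parameters, so they are used here; that mismatch is a separate matter.

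**Step 1: Table 4.** The boundary at n is the smallest x with P(Beta(0.4 + x, 1.6 + n − x) > 0.20) > 0.95. This reproduces every row from 3 to 19. At n = 20 the same formula gives 0.923 for 7 toxicities and 0.972 for 8, so the missing row would be 8-20.

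**Step 2: Table 5.** This is an exact binomial recursion with a look after every patient from 3 to 19, each outcome known at once, and no look at 20.

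| True rate | Pr(stop), recomputed | Stated | Mean N, recomputed | Stated |
|---|---|---|---|---|
| 0.05 | 0.001 | 0.00 | 20.0 | 20 |
| 0.10 | 0.009 | 0.01 | 19.9 | 20 |
| 0.20 | 0.108 | 0.11 | 18.8 | 19 |
| 0.30 | 0.376 | 0.38 | 16.0 | 16 |
| 0.40 | 0.701 | 0.70 | 12.2 | 12 |
| 0.50 | 0.910 | 0.91 | 8.7 | 9 |

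**Step 3: delay against accrual.** The latest confirmation of a toxicity is day 56 (56 days in total, Section 4.4) or about day 28 + 56 = 84 (56 days from the intended start, Section 4.7). The mean gap between patients is 365/10 = 36.5 to 365/5 = 73 days. Further enrolments while one outcome is pending:

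- 10 per year: 56/36.5 = 1.5 to 84/36.5 = 2.3
- 5 per year: 56/73 = 0.8 to 84/73 = 1.2

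**Step 4: Table 4 by enrolment, accrual not paused.** Simulation with toxicity known at day 56 or 84, non-toxic outcomes known at day 28 or at the same lag, and evenly spaced or Poisson arrivals. Ranges cover these variants.

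| Accrual, lag | Pr(stop before 20), rate 0.40 | Rate 0.50 | Mean N, rate 0.40 |
|---|---|---|---|
| Table 5 | 0.70 | 0.91 | 12 |
| 5/year, 56 days | 0.66-0.70 | 0.89-0.91 | 12-13 |
| 5/year, 84 days | 0.62-0.63 | 0.86-0.87 | about 14 |
| 10/year, 56 days | 0.60-0.62 | 0.85-0.86 | about 14 |
| 10/year, 84 days | 0.52-0.55 | 0.80-0.81 | 15.2-15.7 |

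At a true rate of 0.30 the figure is 0.38 for 5 per year, evenly spaced, 56 days, where each outcome is known before the next arrival. It is 0.22-0.34 in every other scenario.

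**Step 5: sparse looks.** Looking only every 2 or every 3 patients, with no delay at all, gives 0.32 or 0.31 at a rate of 0.30, 0.65 at 0.40 and 0.89 at 0.50.

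**Step 6: Table 4 by known outcome.** If toxic and non-toxic outcomes have the same lag, the boundary is ever crossed with probability 0.37-0.38, 0.70-0.71 and 0.91 at 0.30, 0.40 and 0.50, which matches Table 5. Crossing comes later: at 0.40, mean N is up to 13.7. If non-toxic outcomes are known at day 28 and toxic ones at 56-84, the early non-toxic results dilute the count, and the probabilities are 0.30-0.38, 0.63-0.70 and 0.87-0.91.

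**Step 7: a row at 20.** With immediate outcomes, adding 8 of 20 gives 0.387, 0.718 and 0.922, a gain of 1.1 to 1.7 points. With delays and the enrolment index it recovers up to 6, 11 and 9 points, but only after enrolment is complete. At 10 per year, 84 days and a rate of 0.40, 10-12% of simulated trials end with 8 or more toxicities among 20 and no boundary crossed.

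**The case against.** The strongest reply is that the Summary Reports text already supplies a workable denominator. If evaluable means that the toxicity outcome is known, and all outcomes have the same lag, the chance of ever stopping matches Table 5, and the cost is only later stopping with more patients treated. This stands in part, and it shows that the column heading need not be how the trial is run. It does not rescue the plan. Evaluable is undefined, completing Cycle 1 is not the same as having a known outcome, and reports every 2-3 patients lower the stopping probability on their own (Step 5).

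Four stronger readings are tempting, and the documents do not support them:

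- A reader might infer that the rule always stops less often than Table 5. It does not: the shortfall is zero at 5 per year, evenly spaced, with a 56-day lag, and the documents do not say that accrual continues while outcomes are pending.
- A reader might take 56-84 days as the time every outcome needs. It is the maximum for confirming a toxicity. A patient who starts Cycle 2 on time is known to be non-toxic near day 28, and some toxicities could be settled sooner.
- A reader might blame the missing row at 20 for the gap from Table 5. Table 5 itself has no look at 20, so that row explains none of it.
- A reader might say that Table 5 holds only if each outcome is known before the next enrolment. Its stopping probabilities also hold under known-outcome counting with equal lags; its mean sample sizes do not.

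**Conclusion.** The point holds as a conflict and an omission with a measurable, conditional consequence. One section gives two denominators for the same table and says nothing about pending patients or accrual. Table 5 describes per-patient looks with immediate outcomes. Neither the column heading taken literally nor the reporting schedule generally delivers it.

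Under the enrolment reading, the loss in stopping probability runs from 0 to about 16 points at a true rate of 0.30 (0.38 − 0.22) and from 0 to about 18 points at 0.40 (0.70 − 0.52), with mean N at 0.40 up to about 15.7 against 12 stated. The worst case needs 10 patients per year, confirmation at about day 84, uninterrupted accrual and the literal heading together. Arrival pattern, timing within the window and absence of a pause are assumptions. The sparse-look loss needs no assumption about delay.

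The missing row at 20 matters for a different reason. The rule terminates treatment, which under Section 4.2 can run to 24 cycles or longer, and the last outcomes arrive after enrolment has closed.

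**What to change.** - Use one denominator in Table 4 and in the Summary Reports text: patients whose Cycle 1 toxicity outcome is known. A patient with an unresolved event stays out of the denominator until the event resolves or is confirmed.
- State how pending patients are handled and whether accrual pauses for them.
- Add the row for 20 that the stated posterior rule already gives: 8-20.
- Reconcile the wording of the 56-day delay in Sections 4.4, 4.7 and 8.0, so that the time at which a toxicity is confirmed is unambiguous. Which reading applies is for the sponsor to settle.
- Recompute Table 5 for the actual look schedule, the outcome delay and 5-10 patients per year. Report stopping before the 20th enrolment separately from ever crossing.

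The cost is a few text edits and one re-run, with somewhat less favourable figures. With known-outcome counting and the row at 20, the chance of ever crossing at a rate of 0.40 is about 0.66-0.73. That includes crossings after all 20 are enrolled, so it should not be set against the 0.52-0.70 for stopping before 20. Like for like, crossing before the 20th enrolment can be as low as about 0.60 at 10 per year with an 84-day lag and non-toxic outcomes known at day 28, and more patients are treated than Table 5 now states.
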